## 1. PURPOSE OF THE STUDY

---

### a. Brief Summary

This is a pilot, single-site, cohort study at Stanford. The purpose of this pilot study is to assess the feasibility and effectiveness of a mobile technology-based system to assist Providers in managing hypertension remotely using a platform that integrates an FDA-approved home blood pressure monitor with a dashboard that displays patient blood pressure data. Hypertension is a major public health burden and hypertension is often undertreated despite the availability of numerous antihypertensive agents. There is a strong need to promote optimal hypertension management across populations, including timely and effective medication titration to achieve optimal control and prevent future complications including cardiovascular and renal events.

---

### b. Objectives

We aim to assess whether a novel mobile technology-based system will be feasible and effective in helping Providers manage hypertension remotely using a platform that integrates an FDA-approved home blood pressure monitor. Specifically, through this pilot study, we hope to assess how much providers and patients are utilizing the system after implementation, whether antihypertensive medication titration is being effectively performed, and whether blood pressure control is being achieved. This study will generate preliminary feasibility and effectiveness data which will be used to iterate the mobile technology system and will serve as the basis for a subsequent large randomized clinical trial to evaluate the efficacy of this system for remote blood pressure management.

---

### c. Rationale for Research in Humans

The purpose of this study is to test the feasibility and effectiveness of a mobile technology-based system for hypertension management in outpatients with essential hypertension.

---

## 2. STUDY PROCEDURES

---

### a. Procedures

Prespecified Stanford clinics (Internal Medicine, Family Practice, Cardiology, and Hypertension) will undergo implementation of a mobile- technology based system that utilizes a remote home blood pressure cuff system integrated with a physician/APP (advanced practice provider)- facing platform.

First, these clinics will be verbally informed of the study by the study investigators. Treating providers within these clinics will identify potentially eligible patients and will first inform patients and then the study team. The study team will screen the patient for

eligibility by phone and obtain informed consent from the patient and provider if the patient is eligible. The provider will begin use of the mobile technology system for hypertension management for the patient. When enrolling the patient, the provider will indicate the desired future sequence of antihypertensive medication for escalation if needed. Patients will be provided a commercially available, FDA-approved home blood pressure (BP) monitoring cuff (HEM 9200T or HEM 9210T, Omron HealthCare, Inc). These FDA- approved cuffs are used commercially with a mobile application (Omron HeartAdvisor) that stores the patient's raw blood pressure readings from the blood pressure cuffs. Patients will be asked to download this application along with receiving the cuff. Blood pressure cuffs will be purchased by the research team. Patients will be asked to measure their blood pressure twice a week for a total of 12 weeks. Providers will be instructed to see remote BP data through the MyHealth Tracking kit on Epic per current practice. The BP data will also be stored on a dashboard created securely in REDcap. During the study, patients will receive secure messages on a weekly basis through the REDCap system to provide blood pressure measurement reminders, record medication adherence, and record the presence/absence of adverse effects to medications. During the study, the dashboard presents to the physician/APP the changes in medications that the physician/APP has previously decided upon enrollment. Treating providers may use BP data to modify the patient's blood pressure management, act in accordance with these previously selected changes, or make other decisions regarding medications. The study coordinators will maintain a list of participating patients in the secure REDcap system. The pilot study will aim to recruit a total of 50 patients and 10 providers. We will administer surveys to the patients and providers at the end of the study. Prespecified data regarding feasibility and effectiveness will be collected over a followup period of 12 weeks and will be stored in the secure REDcap system for analysis.

Data collected at start of study period: Age, race/ethnicity, Body-mass index, baseline blood pressure, medications, comorbidities (including laboratory results related to comorbidities, such as serum creatinine related to renal dysfunction), treating provider, treating clinic.

Data during and at the end study period: Blood pressure medication changes, reason for medication changes, adherence to medications, and anonymous patient and provider surveys.

The primary outcomes of the study will comprise of the following:

- Blood pressure at 12 weeks compared to baseline blood pressure
- Ease of using the home blood pressure cuff system by patients (through anonymous survey)
- Ease of use of the system by providers (through anonymous survey)

---

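### Does the protocol leave provider use of the system unmeasured, and the provider ease-of-use outcome undefined?

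*Protocol*

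**What the plan says.** Section 1b states the aim: "we hope to assess how much providers and patients are utilizing the system after implementation". It adds whether medication is titrated effectively and whether blood pressure control is reached, and says that the resulting data "will be used to iterate the mobile technology system" ahead of a larger randomized trial.

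Section 2a sets out the data flow. Patients take home readings ("Patients will be asked to measure their blood pressure twice a week for a total of 12 weeks"). For the clinician's view, "Providers will be instructed to see remote BP data through the MyHealth Tracking kit on Epic per current practice"; the readings are stored on a REDCap dashboard too, and that dashboard shows the provider the medication sequence he or she chose at enrollment. Providers may "act in accordance with these previously selected changes, or make other decisions regarding medications".

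On data collection, section 2a says "Prespecified data regarding feasibility and effectiveness will be collected over a followup period of 12 weeks" and "We will administer surveys to the patients and providers at the end of the study". Its list for the study period and its end names medication changes, the reasons for them, adherence, and anonymous surveys of patients and providers.

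Sections 2a and 2g give the same three primary outcomes: blood pressure at 12 weeks against baseline, patients' ease of use of the cuff system, and providers' ease of use of the system.

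**The concern.** Two things look wrong at first reading.

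First, an explicit aim appears to have no measure. Ease of use is not extent of use, and the follow-up list contains no log-in count, dashboard view or frequency question. Medication changes do not fill the gap cleanly, because a change may follow the pre-chosen sequence or be decided on other grounds. If use is recorded neither during the study nor on the survey form, it may not be recoverable. Use recorded elsewhere could not be matched to an anonymous rating either.

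Second, the provider outcome does not say which screen is rated. A provider could comply fully by reading blood pressures in Epic, seldom open the dashboard, and still rate the system highly. The rating might then partly describe an existing tool, while the pilot is meant to inform development of a new one.

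**Working it through.** The protocol states no figure on this point, so the check is a reading of the relevant sections against each other.

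**1. Is a provider-use measure named?** No. The baseline list, the follow-up list and the primary outcomes contain none. That part of the concern is correct.

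**2. Does that silence show the data will not be collected?** No. The follow-up list in section 2a cannot be complete:
- It omits blood pressure during follow-up, although blood pressure at 12 weeks is a primary outcome.
- It omits the adverse-effect records that section 2a says are gathered weekly through REDCap.

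The same section refers to prespecified feasibility data without itemizing them, and extent of use is plainly a feasibility item. The provider survey is listed as a data source, but its questions are not reproduced.

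**3. Is provider use treated differently from patient use?** Less than it seems. Patient use is not named as a measure either; it can be derived from stored readings. The schedule gives 2 per week × 12 weeks = 24 readings per patient, or 24 × 50 = 1,200 for the planned sample. An analyst would use these as denominators without being told. For providers, the sequence chosen at enrollment can be compared with the recorded changes and their reasons. This is only a partial proxy, because a change can agree with the sequence without the dashboard having been opened. A strict test (a measure must be named) fails both patient and provider use. A lenient test (data exist from which something can be derived) gives both a source, the provider's being weaker.

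**4. Which component is rated?**
- Section 1a describes a platform joining the home monitor to a dashboard that displays the readings.
- Section 2a says the clinics will have a system implemented that combines the remote cuff with a provider-facing platform, and that the provider starts using this system for the enrolled patient.
- Viewing in Epic is described as existing practice, so it is not what is newly implemented or begun.
- Section 1b speaks of iterating the system as a whole, not the dashboard alone.

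Read together, the provider outcome rates the whole newly introduced arrangement. The Epic instruction makes the boundary of that arrangement less sharp, but it does not contradict the description.

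**5. Can an effect be sized?** No. The 24 and 1,200 scheduled readings describe workload and quantify no bias in a rating. The protocol gives no rating scale, no expected score and no power calculation.

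**The case for a change.** The strongest case for acting is timing. A SAP governs analysis; which use data are gathered, and which interface an outcome refers to, are settled when the study is set up. A frequency question left off the form cannot be added once providers have answered, and it would cost one or two items. With few raters ("The pilot study will aim to recruit a total of 50 patients and 10 providers"), a few ratings given by people who hardly opened the dashboard could affect the result, and the pilot could not tell easy to use from not used. The patient outcome names its object, the cuff system, whereas the provider outcome uses the bare word system.

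Part of this stands. No provider-use item is written down, medication changes are a weak substitute, and a survey that asked about the Epic view and the dashboard separately would be more informative. But these points concern the content of a survey form that is not shown, and nothing in the protocol prevents the form from including them. Restricting the primary outcome to the dashboard would go further than clarification: it would narrow an outcome the protocol sets at system level, which is a preference about the research question and not the repair of an error.

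**Conclusion.** No change to the plan follows. The observation that provider use is not itemized is correct, but it is missing detail on a non-primary feasibility measure in a single-arm pilot. Whoever writes the provider survey, with the aim in section 1b in front of them, can be expected to ask how often providers used the system. The question of which component is rated is an ambiguity of wording that sections 1a and 2a largely resolve in favor of the newly implemented system as a whole.

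No stated rule or number has been shown to produce a wrong answer, and no effect on the primary outcomes can be quantified from the protocol.

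This conclusion assumes that the unseen survey form, or the prespecified feasibility data mentioned in section 2a, includes some record of provider use. If neither did, the provider half of the utilization aim would rest on the partial proxy of medication changes set against the pre-chosen sequence. The blood pressure comparison and the two ease-of-use outcomes would still be collected as planned, though the provider rating would then have to be read without knowing how much the dashboard was used.

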#### **b. Procedure Risks**

Providers will retain the ability to make all final decisions regarding management thus avoiding inadvertent patient risk and deviations from standard of care.

---

**c. Use of Deception in the Study**

Deception will not be used.

---

**d. Use of Audio and Video Recordings**

No audio or video recording will be used.

---

**e. Alternative Procedures or Courses of Treatment**

All patients will continue to receive standard of care treatment during the study. Providers will make all final treatment decisions based on clinical judgement.

---

**f. Will it be possible to continue the more (most) appropriate therapy for the participant(s) after the conclusion of the study?**

Yes, as we anticipate that patients will continue to receive standard of care therapy, as outlined above.

---

**g. Study Endpoints/Analysis Plan**

The study outcomes will be assessed at the end of 12 weeks of follow-up in all patients. This is a single-arm, single center, pilot study to assess feasibility and effectiveness. No standard of care therapy will be withheld during the study. The primary outcomes of the study will comprise of the following:

- Blood pressure at 12 weeks compared to baseline blood pressure
- Ease of using the home blood pressure cuff system by patients (through anonymous survey)
- Ease of use of the system by providers (through anonymous survey)

No power calculation is used for the study.

---

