**c. Vulnerable Populations**

Children and pregnant women will not be enrolled in this study. For other potentially vulnerable populations who may be enrolled, such as economically disadvantaged populations, this study minimizes risk as it is not anticipated to affect standard of care therapy and care will continue to be directed by their Providers. No additional research-based physical visits or costs to the participants are expected either. In addition, potential benefits for vulnerable populations include a reduced need for participants to visit clinical offices to manage hypertension, thus minimizing financial costs and disruption to daily lives that can be associated with Provider visits.

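### Week-12 blood pressure is promised for all patients, but no step obtains it from a patient who has stopped measuring at home

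*Protocol*

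**What the plan says.** Section 2.g sets the time and population: "The study outcomes will be assessed at the end of 12 weeks of follow-up in all patients". The first primary outcome there is "Blood pressure at 12 weeks compared to baseline blood pressure". Neither the source of the week-12 value (home or clinic) nor a window around week 12 is given.

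Section 2.a describes how blood pressure data arise: "Patients will be asked to measure their blood pressure twice a week for a total of 12 weeks". Readings come from the supplied cuff and its app and are stored on the REDCap dashboard. The scheduled contacts in that section are:

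- A weekly message: "patients will receive secure messages on a weekly basis through the REDCap system to provide blood pressure measurement reminders". It also records medication adherence and adverse effects.
- A closing contact: "We will administer surveys to the patients and providers at the end of the study".

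The same section lists the data to be gathered after baseline: "Data during and at the end study period: Blood pressure medication changes, reason for medication changes, adherence to medications, and anonymous patient and provider surveys". Blood pressure is not in that list, and the surveys are anonymous.

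Section 8.c adds: "No additional research-based physical visits or costs to the participants are expected either". The target size is given in section 2.a: "The pilot study will aim to recruit a total of 50 patients and 10 providers".

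**The concern.** The plan commits to an outcome in every patient, but the only route to it depends on the patient continuing to use the system. Section 1.b makes the extent of that use one of the questions of the pilot, so incomplete use has to be expected.

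Effectiveness and feasibility then become entangled. A patient who disengages drops out of the blood pressure comparison instead of contributing whatever change he or she had. If patients who keep measuring also do better, the reported fall is too favourable. Section 1.b says the pilot's data will be used to refine the system and will underlie a later randomised trial, so a result drawn mostly from persistent users could mislead both.

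This is a matter of trial procedure. An analysis plan can say how missing values are handled, but it cannot supply readings that nobody sought.

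**Working it through.** **Step 1. Can any scheduled step yield a week-12 value from a patient who has stopped measuring?**

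| Step in the protocol | Section | Yields a week-12 value from a stopper? |
|---|---|---|
| Home reading twice a week (2 × 12 = 24 requested per patient) | 2.a | No; this is what has stopped |
| Weekly REDCap message | 2.a | Not as described; it reminds, and no follow-up of non-response is given |
| End-of-study survey | 2.a | No; it is anonymous, so a reading could not be linked to a baseline, and it is not described as asking for one |
| Research visit | 8.c | None expected |
| Routine clinic visit | 2.e, 9.c, 10 | Possibly for some patients; standard care continues, but no visit is scheduled and section 10 expects fewer |

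No scheduled step does so.

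**Step 2. What could that do to the result?** The protocol states no attrition rate, expected change or standard deviation, so there is no figure of its own to reproduce. Let d be the share of enrolled patients without a week-12 value, U the mean change in patients with a value, and S the mean change in those without.

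- All-patient mean change = (1 − d) × U + d × S
- Bias of the observed mean = U − [(1 − d) × U + d × S] = d × (U − S)

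Assumed inputs: U = −10 mmHg; d = 10% to 40%; S = 0, −5 or −10 mmHg. N = 50 is from section 2.a.

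| d | Patients with a value, 50 × (1 − d) | Bias if S = 0 | Bias if S = −5 | Bias if S = −10 |
|---|---|---|---|---|
| 10% | 45 | −1.0 | −0.5 | 0 |
| 20% | 40 | −2.0 | −1.0 | 0 |
| 30% | 35 | −3.0 | −1.5 | 0 |
| 40% | 30 | −4.0 | −2.0 | 0 |

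For example, with d = 20% and S = −5: 0.2 × (−10 + 5) = −1.0 mmHg. A negative bias means that the observed fall is too large. If stoppers fell by more than users, U − S would be positive and the observed fall would be too small.

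**The case against.** The strongest reply is that the protocol never says where the week-12 value comes from. Patients stay under their regular provider, and section 8.c rules out only additional research visits. Clinic readings could therefore supply a value for some stoppers. This stands in part. A reader might infer that the result would come only from patients who kept using the system, and the documents contain no such rule. What they support is weaker: home readings are the only scheduled route, so the result would come mainly from those patients.

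A reader might also infer that patients are not contacted at all at the end. That is wrong, because a survey is planned. It does not close the gap, since it is anonymous and is not described as asking for a reading. The weekly reminders may keep some patients measuring, and nothing in the documents shows that a patient who stops has been ignoring them.

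The size and direction of the bias are also open. Setting the change in stoppers to zero gives only the unfavourable column of the table. Patients whose pressure is controlled might be the ones who stop, which could remove or reverse the bias. This objection stands in full.

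Finally, in a single-arm pilot of 50 patients with no power calculation, incomplete measurement is itself a feasibility finding, and the handling of missing values may be in an analysis plan that is not at hand. Both are true, but neither provides a procedure for seeking the reading.

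**Conclusion.** The point holds as a gap in procedure. The protocol promises a week-12 outcome in every patient and schedules no step that would obtain it from someone who has stopped measuring. That conclusion rests on the text alone and needs no assumption about attrition.

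The consequence is conditional. Under an assumed 10 mmHg fall in users and 10% to 40% missing, the observed fall is overstated by 1 to 4 mmHg if stoppers do not change, by 0.5 to 2 mmHg if they fall 5 mmHg, and by nothing if they fall equally. The documents support no single figure and do not settle the direction.

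A reader might go further and treat every patient without a routine week-12 reading as a non-user of the system. That does not follow. Section 1.b asks how much the system is used, and a patient who measured for 11 weeks and missed the last has used it for most of the study.

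The change is worth making because it is cheap during the trial and cannot be made afterwards.

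**What to change.** In sections 2.a and 2.g:

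1. Name the supplied home cuff as the source of the week-12 blood pressure, and state the window of days that counts as week 12. The source of the baseline value is not stated either, so check that the two match.
2. Add a week-12 outcome contact for every enrolled patient, whether or not still measuring. A dedicated REDCap prompt asks for a reading on the supplied cuff. If none arrives, the existing study coordinators make one call to obtain it.
3. Flag prompted readings. Report how many of those enrolled had a week-12 value through routine use, only after prompting, or not at all.
4. Leave prompted readings out of the utilisation measure, and base that measure on readings over the whole 12 weeks, not on the week-12 reading alone.

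The cost is one extra message per patient and, under the assumed 10% to 40%, at most 5 to 20 calls (50 × 0.10 to 50 × 0.40). No visit, device or additional staff is needed, which fits section 8.c. There are two drawbacks. A prompted reading may differ from routine ones, which is why it must be flagged, and a call will not reach everyone. The report would then at least show how many patients have no value.

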**8. PARTICIPANT POPULATION****a. Planned Enrollment**

We expect 10 providers and 50 patients to be enrolled across the following Stanford clinics: Internal Medicine, Family Practice, Cardiology, and Hypertension.

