**g. Recruitment Details**

Pre-specified Stanford clinics (Internal Medicine, Family Practice, Cardiology, and Hypertension) will be eligible and will be informed of the study verbally by the study investigators. Treating providers will identify potentially eligible patients and will first inform patients and then notify the Study Protocol director about eligible participants.

---

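### Does collecting patient ease of use, a primary outcome, by anonymous survey leave that outcome uninterpretable?

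*Protocol*

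**What the plan says.** Protocol section 2.g lists three primary outcomes: the change in blood pressure, patient ease of use and provider ease of use. The patient item reads "Ease of using the home blood pressure cuff system by patients (through anonymous survey"). The same section sets time and population: "The study outcomes will be assessed at the end of 12 weeks of follow-up in all patients".

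Section 2.a repeats the three outcomes in the same terms. Its list of data gathered during and at the end of the study includes "adherence to medications, and anonymous patient and provider surveys". On timing it says "We will administer surveys to the patients and providers at the end of the study", and on home measurement "Patients will be asked to measure their blood pressure twice a week for a total of 12 weeks". It also says that readings are held in REDCap, that coordinators keep a list of participants there, and that patients receive weekly messages through it.

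Section 8.a gives the size: "We expect 10 providers and 50 patients to be enrolled across the following Stanford clinics". Section 8.g gives the route of entry: "Treating providers will identify potentially eligible patients and will first inform patients". Section 1.b gives the purpose: "This study will generate preliminary feasibility and effectiveness data which will be used to iterate the mobile technology system". It also says that the results will be the basis for a later randomized trial.

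No section describes a survey code, a linkage key or a record of who returned the form. None rules out such a record.

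**The concern.** Ease of use is a primary outcome and is meant to cover every patient. Patients who find the cuff or the app awkward may be the ones who stop measuring and also leave the form unanswered. If so, the share reporting that the system is easy would be too high, and that figure would feed the redesign and the later trial.

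The usual safeguard is to compare those who answered with those who did not, on baseline data and on readings sent. Those data sit in REDCap under each patient's name, but anonymous answers cannot be joined to them. Without a return record the team would not even know whose answers are missing. How the data are collected is settled in the protocol, and an analysis plan cannot recover a link that was never recorded. It is therefore fair to ask whether the protocol has fixed this badly, even though the SAP is not at hand.

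**Working it through.** The protocol gives no response rate, success threshold or power calculation for the survey, so there is no figure of its own to reproduce. The check has two parts.

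**1. The text**

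- *Consistency.* Sections 2.a and 2.g name the same outcome and the same anonymous survey. There is no contradiction.
- *Is the lost link needed?* Section 1.b sets out to assess use of the system, medication titration and blood pressure control. Use can be measured from the stored readings without the survey. Ease of use is a separate outcome, and no section plans to analyse it against recorded use.
- *Is the survey restricted to patients still measuring?* No. Section 2.g covers all patients, and section 2.a sends surveys to the patients at the end of the study. Someone who stopped measuring is still due a form.
- *Is a return record excluded?* No. Coordinators already hold a participant list in REDCap. A tick for form returned, kept apart from the answers, is compatible with anonymity and with every section.

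**2. What the numbers measure**

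Inputs from the protocol: N = 50 patients and 2 × 12 = 24 planned readings each. Assumed, because the protocol gives neither: the number of returns n and the number e who answer easy.

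The share answering easy among all 50 lies between e/50 (no non-responder finds it easy) and (e + 50 − n)/50 (all of them do). The width is (50 − n)/50, or 2 percentage points per missing form.

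| n returned | e easy | Share among returned | Lower | Upper |
|---|---|---|---|---|
| 50 | 45 | 90% | 90% | 90% |
| 40 | 36 | 90% | 36/50 = 72% | (36 + 10)/50 = 92% |
| 30 | 27 | 90% | 27/50 = 54% | (27 + 20)/50 = 94% |

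The width depends only on n. Coding the forms or logging the returns leaves it unchanged for a given n. These ranges show what missing forms cost, whatever the type of survey.

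What a return log could add, for an assumed split of 40 responders and 10 non-responders:

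- If 30 of 40 responders and 2 of 10 non-responders sent at least 18 of the 24 readings (75% against 20%), Fisher's exact test gives p = 0.002.
- If the figures were 28 of 40 and 5 of 10 (70% against 50%), it gives p = 0.28.
- For a continuous measure, the difference detectable with 80% power at two-sided 5% is about 1.0 SD.

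The comparison would therefore be descriptive, and only a gross imbalance would show. Similar use in the two groups would not prove similar opinions either.

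**The case for a change.** The strongest case for the concern is that anonymity belongs to data collection and not to analysis. Once the forms are in, the link to readings is gone for good. The same is true of knowing who answered, if nobody kept a record. Use of the system is a stated objective, the use data already exist patient by patient, and a log would cost almost nothing. It would also allow reminders aimed at those who have not answered, and more returns are the one thing that narrows the ranges above.

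Part of this stands. Read literally, an anonymous survey does prevent individual answers from being set against recorded readings, and no SAP can undo that. But no section relies on that link. The only way to keep it is a coded, confidential survey. Patients who came into the study through their own provider may answer a coded form less frankly, which could push reported ease upward, the same direction as the feared non-response bias. That is a trade-off between two designs, and the protocol chose a defensible side.

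The log is a sensible habit. It is, however, an operational detail that a protocol of this kind need not spell out, and its absence from the text does not show that none will be kept. Comparing responders with non-responders is commonly left to the SAP, which is not shown here.

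**Conclusion.** The concern does not hold. The protocol is consistent on this outcome, and following it as written yields a valid descriptive result: ease among the forms returned, with the number returned out of 50. The lost link to readings serves no planned analysis, and the 72–92% and 54–94% ranges reflect assumed non-response, which anonymity does not create. In a single-arm pilot of 50 patients without a power calculation, a return log is a matter of preference and would not change what the study can conclude.

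This rests on two readings. First, anonymous is taken literally; if the sponsor means coded or de-identified forms, the link exists and the question disappears. Second, the protocol's silence on a return log is not taken as a decision against one. If all 50 forms come back there is no non-response to examine, and only the unplanned link to readings is missing.
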